12.3 Sample size calculation

To achieve a power of 80% with a significance level of 0.05, 32 patients will be needed in each treatment arm. A comparative study looking at pain scores following corticosteroid use in transoral robotic surgery reported a standard deviation in VAS pain scores of 2.0 [10]. A 1.2-point difference in VAS pain scores between intervention and control groups would be significant [10,11]. Analysis will be conducted using analysis of Covariance techniques which include pre-surgical pain scores.

The following sample size calculation was conducted for our continuous pain VAS outcome measure:

$$n = \frac{2 [(a + b)^2] \sigma^2}{\delta^2}$$

Where: n = the sample size in each group arm, a = the conventional multiplier for alpha (1.96 for 5% alpha), b = the conventional multiplier for power (0.84 for 80% power), σ = standard deviation and δ = the difference you wish to detect.

$$n = \frac{2 [(1.96 + 0.84)^2] 2^2}{1.2^2}$$

$$n = \frac{62.72}{1.96} = 43.5 \text{ patients per overall}$$

$$= 87 \text{ patients in total}$$

To account for the study using pre-surgical pain scores in the final analysis, the sample size is adjusted using a design factor based on the correlation between pre- and post-surgical pain scores. Here a conservative estimate of 0.3 is used. A final sample size, including 5% inflation for patient attrition is then given by:

$$87 * (1 - 0.3) * 1.05 = 64 \text{ patient (32 per treatment group)}$$

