11.3 Participant withdrawal

By consenting to this trial, participants are accepting of the trial interventions, assessments and follow up data collection requirements. However, at time of informed consent, patients will be reminded that their participation is voluntary, and they retain the right to withdraw from the study without reason and without prejudicing any further treatment. The sample size calculation accounts for some participant withdrawal, so it is not anticipated that it will be necessary to replace participants who decide to withdraw.

If a participant does decide to withdraw from this study, they can do so at any time by informing the CI or any other member of the research study team by calling [name]. The contact details of the study team are recorded on the PIS. The investigator will need to clarify whether the participant wishes to withdraw from all or only particular trial components. If the latter is requested, then follow up data collection for which the participant previously consented to may continue. Should any participant wish to withdraw fully from the study, any data collected prior to withdrawal may be retained and used in trial analysis as specified by the study protocol. If following randomisation, the participant does not go on to have their surgery they should be withdrawn from the trial.

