12.4 Statistical analysis

All data will be collected using the trial CRF and will be included in the final analysis. A detailed statistical analysis plan will be developed before the analyses are conducted. The following statistical considerations will be used in this study:

Data Summaries:

Continuous data are summarised as median (inter-quartile ranges) and categorical data are summarised as frequencies of counts (percentages). All VAS pain scores will be recorded to 1 decimal point.

Missing Data:

Missing data are assumed to be rare given the study methodology and short follow up period, and analyses are thus planned on a complete case basis.

Levels of Significance:

Statistical significance will be determined using the $p < 0.05$ significance level with all results presented alongside two-sided 95% confidence intervals.

Patient groups for analysis:

All analysis will be carried out on an intention to treat basis, retaining patients irrespective of any protocol violations.

Analysis of the primary outcome:

Analysis of the primary outcome will be carried out using Analysis of Covariance (ANCOVA) techniques. Here the post-operative pain score will be analysed as the primary outcome with the pre-surgical pain score being included as an adjusting covariate. Results will be presented in terms of the difference in means (95% confidence) intervals between the two groups.

13 Informed consent, ethical and regulatory considerations

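### Section 12.3 shrinks the sample by (1 - 0.3) where an ANCOVA with pre/post correlation 0.3 allows only 1 - 0.3² = 0.91, so 64 patients give about 69-71% power, not 80%

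*Combined protocol and SAP*

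**What the plan says.** Section 12.3 makes the claim "To achieve a power of 80% with a significance level of 0.05, 32 patients will be needed in each treatment arm". It rests on an SD of 2.0 VAS points, a target difference of 1.2 points and the usual normal-approximation formula for two means, which gives 87 patients in total before any adjustment. Then "the sample size is adjusted using a design factor based on the correlation between pre- and post-surgical pain scores", followed by "Here a conservative estimate of 0.3 is used". The last line applies the factor and a 5% attrition allowance: "87 * (1 - 0.3) * 1.05 = 64".

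Section 12.4 sets the primary analysis as an ANCOVA of the post-operative score, "with the pre-surgical pain score being included as an adjusting covariate". On missing data it says "analyses are thus planned on a complete case basis". Section 11.3 adds "The sample size calculation accounts for some participant withdrawal" and does not expect to replace those who withdraw.

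**The concern.** The only quantity named before the value 0.3 is the pre/post correlation, so the natural reading is r = 0.3. Adjusting for one baseline covariate leaves a residual variance of (1 - r²) times the unadjusted variance. A correlation of 0.3 therefore saves 9% of the sample, whereas the protocol takes off 30%. A deliberately cautious correlation ought to yield a small saving, and the factor used removes that caution.

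The 80% figure is the only justification given for 32 per arm. If it is wrong, the trial is more likely than stated to miss a true 1.2-point difference, and a null result could be read as adequately powered evidence of no benefit. There is no slack elsewhere: losses are not to be replaced and the analysis is complete case, so the power after 5% loss is the planned scenario.

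**Working it through.** **Inputs.** From section 12.3: σ = 2.0, δ = 1.2, multipliers 1.96 (two-sided 5%) and 0.84 (80% power), correlation 0.3, attrition 5%. From section 12.1: 1:1 allocation. From section 12.4: ANCOVA of a post-operative score on the pre-surgical score, two-sided intervals.

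**1. The protocol's own figure.**
- n per arm = 2 × (1.96 + 0.84)² × 2² / 1.2² = 62.72 / 1.44 = 43.56, so 87 in total.
- 87 × 0.70 × 1.05 = 63.9, i.e. 64.

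The stated 64 is reproduced, but only with the factor 0.70. The denominator in the last step is printed as 1.96, which does not match the 1.2² in the line above. 62.72 / 1.96 would be 32.0, not 43.5, so 1.44 was used and 43.5 and 87 are unaffected.

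**2. The factor for the planned analysis.**
- ANCOVA: 1 - r² = 1 - 0.09 = 0.91.
- Correlation that would give 0.70: r = √0.30 = 0.55.
- An analysis of change scores would have factor 2(1 - r) = 1.4, which raises the sample size, so it does not explain 0.70 either.

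**3. Sample size with 0.91.** 87 × 0.91 × 1.05 = 83.1, so 84 patients (42 per arm).

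**4. Power of 64 patients at r = 0.3.** Residual SD = 2 × √0.91 = 1.908. Power = Φ(δ / (SD × √(2/n)) - 1.96).
- No loss, n = 32 per arm: SE = 1.908 × √(2/32) = 0.477; 1.2 / 0.477 = 2.516; Φ(0.556) = 71.1%.
- 5% loss, n = 30.4 per arm: SE = 1.908 × √(2/30.4) = 0.489; 1.2 / 0.489 = 2.452; Φ(0.492) = 68.9%.
- By the noncentral t distribution with 2n - 3 degrees of freedom: 69.7% and 67.4%.
- Simulated ANCOVA, 40,000 trials each: 68.8% with 64 analysed, 66.7% with 61 analysed.

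**5. Difference detectable with 80% power.** 2.80 × 1.908 × √(2/n) = 1.34 points with no loss and 1.37 points after 5% loss.

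**6. Check of 84 patients.** After 5% loss (39.9 per arm) power is 80.2% by the normal approximation and 79.2% by noncentral t.

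**7. Sensitivity to the correlation.** The protocol gives no source for 0.3, so the range for 64 randomised (normal approximation) is:

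| r | Power, no loss | Power, 5% loss |
|---|---|---|
| 0 | 67% | 65% |
| 0.2 | 69% | 67% |
| 0.3 | 71% | 69% |
| 0.4 | 74% | 72% |
| 0.5 | 79% | 77% |
| 0.55 (r² = 0.30) | 82% | 80% |

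To reach 80% with 64 randomised, r must be about 0.52 with no loss or 0.55 after 5% loss.

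**The case against.** The strongest defence is that 0.3 was meant as the squared correlation. The text says the factor is based on the correlation and never writes r = 0.3. If 0.3 is r², then 0.70 is the right ANCOVA factor and 64 follows by the protocol's method. This cannot be ruled out, but it is not what the words say, and it needs a correlation of about 0.55 for which no source is given. Section 12.3 therefore needs correcting on either reading.

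A second defence is that pain is scored on six post-operative occasions (section 12.2.1) and section 12.4 does not name a day. Combining several scores would change the variance factor. That is true, and the figures here assume a single post-operative score. But section 12.4 describes one score with no averaging and no repeated-measures model, and section 12.3 takes no credit for repeats.

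Third, 69-71% comes from the normal approximation, and the t-based figures are a point or two lower. The protocol uses the normal approximation, so the comparison with its 80% is like for like, but any restated power should name the method.

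Finally, the documents do not show how 1.96 came to stand in the denominator. What can be said is that it conflicts with the line above and has no effect on the result.

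**Conclusion.** The concern holds. As written, section 12.3 applies a factor of 0.70 where a correlation of 0.3 and the planned ANCOVA give 0.91. On the stated inputs, 64 patients give 71% power with no loss and 69% after the planned 5% loss (70% and 67% by noncentral t). The risk of missing a true 1.2-point difference is therefore 29% to 31%, not 20%.

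This rests on three assumptions: 0.3 is the correlation, the primary analysis uses one post-operative score, and the SD is 2.0. If 0.3 is the squared correlation, the stated 64 stands by the protocol's method, at 80% power after loss. The protocol would then have to say so and support it.

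**What to change.** Amend section 12.3 in one of two ways.

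1. **If 0.3 is the correlation**, replace (1 - 0.3) with (1 - 0.3²) = 0.91 and restate what 64 patients deliver. Suggested wording: *With an SD of 2.0 and a pre/post correlation of 0.3, 64 patients give 69% power (5% loss) to 71% power (no loss) by the normal approximation for a 1.2-point difference, or 80% power for a difference of 1.37 to 1.34 points; 80% power for 1.2 points would need 84 patients.* If the sponsor wants to keep 80% power for 1.2 points, the target becomes 84.
2. **If 0.3 is the squared correlation**, say so and cite a source for a pre/post correlation of about 0.55. The 64 then stands.

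In the same edit, change the denominator 1.96 to 1.44; 43.5 and 87 stay as they are.

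The cost is wording in section 12.3. Option 1 makes the stated power less favourable but needs no more patients unless the sponsor chooses to enlarge the trial, which would add 20 (84 - 64). Option 2 costs finding a source.

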12.4 Statistical analysis

All data will be collected using the trial CRF and will be included in the final analysis. A detailed statistical analysis plan will be developed before the analyses are conducted. The following statistical considerations will be used in this study:

Data Summaries:

Continuous data are summarised as median (inter-quartile ranges) and categorical data are summarised as frequencies of counts (percentages). All VAS pain scores will be recorded to 1 decimal point.

Missing Data:

Missing data are assumed to be rare given the study methodology and short follow up period, and analyses are thus planned on a complete case basis.

Levels of Significance:

Statistical significance will be determined using the $p < 0.05$ significance level with all results presented alongside two-sided 95% confidence intervals.

Patient groups for analysis:

All analysis will be carried out on an intention to treat basis, retaining patients irrespective of any protocol violations.

Analysis of the primary outcome:

Analysis of the primary outcome will be carried out using Analysis of Covariance (ANCOVA) techniques. Here the post-operative pain score will be analysed as the primary outcome with the pre-surgical pain score being included as an adjusting covariate. Results will be presented in terms of the difference in means (95% confidence) intervals between the two groups.

13 Informed consent, ethical and regulatory considerations

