5.4 Exclusion criteria

Patients are not eligible for the trial if **any** of the following criteria apply:

- Lesions undergoing incisional or punch biopsy only.
- Surgery with planned primary closure or local/ distant flap reconstruction.
- Inability to provide written informed consent.

- Medical contraindication to a general anaesthetic or to PuraBond® use.

6 Surgery

Surgery should only be carried out through the transoral route. Depending on the lesion subsite, suitable procedures include:

Oral cavity

Excision of a lesion from free oral mucosal surfaces with planned healing by secondary intention.

Oropharynx:

- Tonsillectomy
- Tongue base mucosectomy
- Lateral oropharyngectomy
- Tongue base resection
- Soft palate excision

It is important to note that all surgical procedures undertaken will be standard of care and agreed on before and regardless of trial participation. PuraBond® is already in use in head and neck surgery at LUHFT depending on the operating surgeon's preference and is currently on the recognised supplier list for the trust.

7 Registration and randomisation

Following clinical assessment, participants will be randomised to one of two trial arms using the method of minimisation. Randomisation will be performed centrally by the LCTC. Patient eligibility must be established prior to randomisation (see section 5.1) and patients must confirm their consent by providing a signed informed consent form (see section 12.1). Details of the trial enrolment will be recorded in the participant's electronic patient record. This will include confirmation of eligibility and the date of enrolment into the trial.

At registration the participant will be given a unique participant trial number. At randomisation the participant will be allocated to a treatment arm. To register or randomise a patient the relevant registration or randomisation case report form (CRF) should be completed and the LCTC contacted. Participants will be randomised centrally by a computer in a 1:1 ratio to either have PuraBond® applied to the surgical field or not intraoperatively. A minimisation algorithm will be used within the online randomisation system to ensure balance in the treatment allocation over the three following clinical variables:

- Surgical subsite: oral cavity or oropharynx
- Surgical operation: concurrent neck procedure (yes or no)
- Surgical technique: laser use (yes or no)

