The operating surgeon will be informed by LCTC regarding the patient's treatment arm allocation. Due to the packaging of PuraBond® within pre-filled and labelled syringes, attempts to completely blind clinicians intraoperatively are not feasible. However, the patient, the assessors of postoperative outcomes and the study co-investigators will be blinded.

8 Trial endpoint assessments

The aim of the PuraBond® PROOF trial is to determine whether PuraBond® application intraoperatively on the surgical field significantly reduces postoperative pain in head and neck transoral operations. Assessment of secondary clinical outcomes such as hospital stay and time till oral intake alongside post operative complications are also important points to record consequently. The study will also briefly consider any health economic benefits of PuraBond® use.

Details of the assessments required are included in the CRF and are outlined below in the schedule of trial assessments (see section 8.4). With regards to the timing of assessments, the date of transoral surgery and thus whether PuraBond® is applied or not is classified as day 0.

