9.2.1 Adverse Events (AE)

An AE has been defined above (see section 9.1). It may or may not be related to the transoral surgical procedure or PuraBond® application to the surgical field. Any AE should be recorded, this can be done on the designated CRF and in the patient electronic hospital medical records.

A list of expected complications of transoral surgery include:

- Teeth, lip, gum injury
- Cutaneous or intraoral laser injury
- Pain
- Haemorrhage
- Surgical site infection
- Velopharyngeal insufficiency
- Difficulty swallowing
- Lingual or hypoglossal nerve injury

- Pharyngocutaneous fistula

A list of expected complications of PuraBond® application include:

- Irritation/inflammation, or disruption of blood components, due to the low pH of the product.
- Thromboembolism following migration of thrombus resulting from haemostatic effect.
- Embolization of gelled product following migration into blood vessels before or after gelation.

The above listed complications can be used as the RSI when assessing the expectedness of SAEs causally to the trial treatments.

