12.2.2 Secondary outcome measures

This will include data on:

- Post-operative analgesia usage (including drug used, dose, route and frequency)
- Post-operative complications by Clavien Dindo Classification including wound infection and bleeding rates
- Length of stay in hospital
- Readmission to hospital within 30 days post operatively
- Bleeding events including primary (24 hours post operatively) and secondary (day 1 to 30 post operatively) haemorrhage
- Return to operating room within 24 hours post operatively
- Return to operating room within 30 days post operatively
- Surgeon survey regarding ease of PuraBond® use
- Time taken to normal oral dietary intake (days)
- Any health economic benefits of PuraBond® use.

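### With every analysis by intention to treat and no safety set, a PuraBond-specific harm in any control patient who received the product would be summarised under the control arm

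*Combined protocol and SAP*

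**What the plan says.** **Analysis population.** Section 12.4 gives one rule: "All analysis will be carried out on an intention to treat basis, retaining patients irrespective of any protocol violations". Neither a safety set nor a set defined by treatment received appears anywhere in the document. The same section says that data collected on the CRF enter the final analysis, and Section 9.2.1 has adverse events recorded on the CRF. It also defers detail: "A detailed statistical analysis plan will be developed before the analyses are conducted".

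**Harms.** Section 12.2.2 lists as a secondary outcome "Post-operative complications by Clavien Dindo Classification including wound infection and bleeding rates". Section 9.2.1 lists three expected complications of the product itself: irritation, inflammation or disruption of blood components; thromboembolism; and "Embolization of gelled product following migration into blood vessels before or after gelation".

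**Access to the product.** Section 6 says that "PuraBond® is already in use in head and neck surgery at LUHFT depending on the operating surgeon's preference" and that it is "currently on the recognised supplier list for the trust". Section 7 says that "attempts to completely blind clinicians intraoperatively are not feasible", and that the surgeon is told the allocation.

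**Recording of use.** The intra-operative data in Section 8.2 and the schedule in Section 8.4 contain no explicit item for whether PuraBond was applied. The surgeon's survey might capture it, but its content is not given.

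**The concern.** Intention to treat is the right basis for the pain comparison, which asks about the effect of allocation. A harm that only exposure to the product can cause raises a different question. If such a harm occurs in a control patient who was given PuraBond, the Section 12.4 rule places it in the control column. An allocated patient who never received the product stays in the PuraBond denominator. Both movements pull the difference in device harms towards zero, so a safety summary could look more reassuring than the exposed patients' experience warrants.

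The conditions for crossover exist: the product is to hand, its use is a matter of surgeon preference outside the trial, and the surgeon is unblinded. The document does not say how its use in a control patient would be analysed.

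Case-by-case reporting covers only part of the gap. Section 9.2.2 exempts hospitalisation for the listed complications from expedited reporting. It requires reports to the ethics committee only for events that are both related and unexpected. The three product-specific events are on the expected list.

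**Working it through.** **Inputs.** The documents supply 32 patients per arm (Section 12.3) and 1:1 allocation (Section 12.1). They give no crossover rate and no device-harm rate, so every such value below is an assumption.

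**The plan's own figure.** 2 × (1.96 + 0.84)² × 2.0² / 1.2² = 62.72 / 1.44 = 43.56 per arm, about 87 in total. Then 87 × (1 − 0.3) × 1.05 = 63.9, so 64, or 32 per arm. The stated total reproduces, and nothing in this point changes it.

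**Attenuation.** Let *b* be the background risk, *h* the excess risk from exposure (the same for everyone exposed), *x* the share of controls exposed and *u* the share of the PuraBond arm unexposed.

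- Risk in the PuraBond arm: b + h(1 − u)
- Risk in the control arm: b + hx
- Intention-to-treat difference: h(1 − u − x)

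| Controls exposed (x) | PuraBond arm unexposed (u) | Share of true excess kept |
|---|---|---|
| 10% | 5% | 1 − 0.05 − 0.10 = 85% |
| 20% | 5% | 1 − 0.05 − 0.20 = 75% |
| 30% | 10% | 1 − 0.10 − 0.30 = 60% |

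**In patients, with crossover from control only.** If *c* of 32 controls are exposed, the share kept is 1 − c/32. The chance that at least one device harm falls in the control arm is 1 − (1 − h)^c, taking background risk as zero.

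| c | Share kept | Difference at h = 10% (points) | Difference at h = 5% (points) | Chance, h = 10% | Chance, h = 5% |
|---|---|---|---|---|---|
| 1 | 96.9% | 9.7 | 4.8 | 10% | 5% |
| 3 | 90.6% | 9.1 | 4.5 | 27% | 14% |
| 6 | 81.3% | 8.1 | 4.1 | 47% | 26% |
| 10 | 68.8% | 6.9 | 3.4 | 65% | 40% |

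At an assumed device risk of 1%, the chance is 1 − 0.99³ = 3% with three crossovers and 1 − 0.99⁶ = 6% with six.

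**Counts.** Take two device harms in the PuraBond arm and one in a single crossed-over control. Intention to treat shows 2/32 (6.3%) against 1/32 (3.1%). By product received it is 3/33 (9.1%) against 0/31. If the only event is in the crossed-over control, the tables read 0/32 against 1/32 and 1/33 against 0/31, and the direction changes.

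**The case against.** **The plan is openly incomplete.** A detailed SAP is promised, and safety populations are usually set there. Device-specific events are not named as outcomes and no comparative adverse-event table is described, so they come under the rule only through its reach over all analysis and through the complications outcome. This stands as a limit on certainty. It does not remove the point, because a SAP that followed Section 12.4 literally would have no safety set.

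**Other safeguards exist.** A reader might infer that, without an IDMC, the final harms table is the main safety output. The documents do not support that. Section 11.1.2 sets up an independent Trial Steering Committee. Section 9.2.2 has the sponsor informed of any SAE, and relatedness is considered when deciding on ethics committee reports. A serious event in a control patient could therefore be attributed to the product. These routes do not correct a summary by arm, and they do not cover non-serious irritation or inflammation.

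**Crossover may be rare.** Section 7 allocates patients to application or none, so use in a control would be a departure from protocol that Section 11.5 requires to be reported to the sponsor. Section 11.3 withdraws patients who never have surgery, which removes one source of unexposed patients. It is also tempting to infer that a control who bleeds is the likeliest to be given a haemostat. That is plausible from the product's purpose, but nothing in the documents says so.

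**Grouping by product received has its own bias.** If bleeding did prompt crossover, tabulating all adverse events this way would move those patients into the device column and count haemorrhage and non-specific events against PuraBond. This objection is sound and limits the remedy to the listed product-specific events.

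**Conclusion.** The point holds conditionally. The stated rule would assign a device-specific harm in an exposed control to the control arm, and no other analysis set would show it. Under constant device risk and the three assumed crossover patterns, 85%, 75% or 60% of the true excess remains. Crossover and harm rates are both undocumented, so the real loss could be negligible.

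Two stronger readings should be resisted. The documents do not show that crossover will happen, so it cannot be said that harms will be miscounted. And although one event can change the direction of a small table, this mainly shows that 32 per arm cannot compare rare harms reliably under either grouping. The primary pain analysis and the sample size are unaffected. The change is worth making because it is conventional and cheap.

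**What to change.** 1. Keep intention to treat in Section 12.4 for pain, bleeding, return to theatre and all other outcomes.
2. Add a CRF item on the day of surgery, completed for every patient in both arms, recording whether PuraBond was actually applied, and show it in Sections 8.2 and 8.4. The blinding in Section 7 of outcome assessors and co-investigators should be protected when this item is stored.
3. Add to Section 12.4 wording such as: *In addition to the intention-to-treat summaries, the PuraBond-specific events listed in Section 9.2.1 (irritation/inflammation, thromboembolism, gel embolisation) will be tabulated by product received (any PuraBond applied or none). This table is descriptive and non-randomised. Patients whose treatment differed from allocation will be listed individually.*

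The cost is one CRF item and one extra descriptive table. That table can be confounded by the reason for crossover, particularly for irritation or inflammation, which surgery alone may cause, so it should carry no formal test. If no crossover occurs, it repeats the intention-to-treat table and documents that fact.

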3.2 Study objectives

The aim of this study is to assess whether intraoperative use of the haemostatic agent PuraBond® is associated with decreased levels of pain postoperatively following wide local excision procedures for oral or oropharyngeal mucosal lesions. We hypothesise that patients treated with such agents will have better post-operative pain scores compared to those treated without.

4 Study design

PuraBond® PROOF is a prospective, single centre, parallel group randomised controlled trial (RCT). Patients eligible for the study must have clinically suspected or histologically confirmed dysplasia or malignancy in the oral cavity or oropharyngeal subsites. Their primary lesion must be considered resectable via a transoral approach. After informed consent, patients will undergo baseline assessment of pain levels prior to surgery and demographic data will be collected. Surgery may or may not involve laser use to the primary site.

Suitable patients will be stratified prior to randomisation by lesion site (oral cavity or oropharynx) and whether or not the surgical technique will involve laser resection. Depending on which arm the participant is allocated to, PuraBond® may or may not be applied to the surgical bed intraoperatively. It is important to note that both treatments are routinely used in these operations and PuraBond® use will fall completely within its license in this study.

Using surgical site and technique to clinically stratify patients is important as standard post operative analgesia management differs between these groups (see table below). It is important that data collected from this trial represents real world evidence and thus, pre and post operative analgesia agents used will be recorded by analysing patient's prescriptions rather than. restricting analgesia prescriptions and changing current standard of care. This means this trial will not lack generalisability and will not limit the relevance of its results to real world practice.

Medication	Oropharyngeal surgery		Oral cavity surgery
	TOLR	No laser used	
Paracetamol	✓	✓	✓
Ibuprofen	✓	✓	✓
Codeine	✓	✓	✓
Morphine	✓	Not routinely used	Not routinely used
Oxycodone	X	Not routinely used	Not routinely used
Chlorhexidine	X	X	✓
Gelclair®*	✓	X	✓
Benzydamine 0.15% solution	✓	✓	✓
Pregabalin	✓	X	X

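### The trial minimises on subsite, neck procedure and laser use, but the primary ANCOVA names only pre-surgical pain as a covariate, which forgoes precision if those factors predict pain

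*Combined protocol and SAP*

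**What the plan says.** Section 7 describes the allocation: "A minimisation algorithm will be used within the online randomisation system to ensure balance in the treatment allocation over the three following clinical variables". The three variables are surgical subsite (oral cavity or oropharynx), concurrent neck procedure (yes or no) and laser use (yes or no).

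Section 4 describes the same step with two factors only. Patients are to be "stratified prior to randomisation by lesion site (oral cavity or oropharynx) and whether or not the surgical technique will involve laser resection". It gives the reason: "Using surgical site and technique to clinically stratify patients is important as standard post operative analgesia management differs between these groups". Section 12.1 mentions site and technique as examples of the balancing factors and does not claim a full list.

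On the analysis, section 12.3 says: "Analysis will be conducted using analysis of Covariance techniques which include pre-surgical pain scores". Section 12.4 says that the post-operative score is analysed "with the pre-surgical pain score being included as an adjusting covariate". It also says: "A detailed statistical analysis plan will be developed before the analyses are conducted". Nowhere do the documents say that the minimisation factors enter the model.

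**The concern.** Minimisation makes the arms alike on the chosen factors. If those factors are related to pain, the treatment difference then varies less from trial to trial than under simple randomisation. A model without the factors leaves their variation in the residual and computes its standard error as if the arms could still differ on them by chance. The reported standard error therefore exceeds the true one.

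The effect goes in one direction. The point estimate is unbiased and the test rejects too seldom under the null, not too often. What is at stake is precision that the design has already secured: the 95% interval is wider than it need be, and power is below what a model with the factors would give. This is gain forgone, not power lost against the plan's own model. If the factors are unrelated to pain, almost nothing changes.

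Section 4 makes a relation plausible for site and laser use, since standard analgesia differs between those groups, but it does not say that pain scores differ. No specific reason is given for neck procedure.

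**Working it through.** **Inputs from the documents.** SD 2.0, target difference 1.2, pre/post correlation 0.3, two-sided 5% level, 5% attrition, 64 randomised 1:1 (section 12.3; section 7 for the ratio; section 12.4 for two-sided intervals).

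**The plan's own figure.** n per arm = 2 × (1.96 + 0.84)² × 2² / 1.2² = 62.72 / 1.44 = 43.56, or 87 in total. Then 87 × (1 − 0.3) × 1.05 = 63.9, so 64. The stated total reproduces. (The printed denominator is 1.96, but the stated 43.5 corresponds to 1.44. That is a separate matter.)

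**Assumptions not in the documents.**
- R², the share of post-operative VAS variance explained by the factors: 0%, 5%, 10%, 20% and 30%, split equally between them.
- Biased-coin minimisation with probability 0.8.
- Three independent binary factors with prevalences 0.5, 0.4 and 0.4.
- Pre-surgical VAS unrelated to the factors (relaxed below).
- 5% random loss, leaving 61 evaluable.

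**What R² means in VAS points.** With three factors sharing R² equally, each shifts VAS by √[(R² × 4 / 3) / (p(1 − p))]. At R² = 10% and p = 0.5 this is √(0.1333 / 0.25) = 0.73, and at p = 0.4 it is 0.75. R² of 5%, 10%, 20% and 30% needs shifts of about 0.5, 0.75, 1.0 and 1.3 points per factor, or about 0.65, 0.9, 1.3 and 1.6 if only site and laser use matter. The target difference is 1.2, so the upper values are large effects.

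**Approximate standard errors.** The baseline-only model has residual variance 4 × (1 − 0.3²) = 3.64, so SE ≈ √(4 × 3.64 / 61) = 0.489. With the factors it is 4 × (0.91 − R²). At R² = 20% that is 2.84, so SE ≈ √(4 × 2.84 / 61) = 0.432.

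**Simulation, 100,000 trials per scenario.**

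| R² | Baseline-only: model SE / true SD | SE overstated | Type I error | Power, baseline-only | Power, factors added | Change (points) | 95% CI half-width, without → with |
|---|---|---|---|---|---|---|---|
| 0% | 0.491 / 0.493 | about 0% | 5.05% | 67.0% | 66.5% | −0.5 | 0.98 → 0.99 |
| 5% | 0.491 / 0.482 | 2% | 4.49% | 67.3% | 69.0% | +1.7 | 0.98 → 0.96 |
| 10% | 0.492 / 0.470 | 5% | 4.00% | 67.6% | 71.5% | +3.9 | 0.98 → 0.93 |
| 20% | 0.492 / 0.446 | 10% | 3.04% | 68.4% | 76.9% | +8.5 | 0.98 → 0.87 |
| 30% | 0.492 / 0.420 | 17% | 2.21% | 69.3% | 83.0% | +13.7 | 0.99 → 0.81 |

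With the factors in the model, type I error is 5.03% throughout. Bias of the baseline-only estimate is below 0.002 points. If only site and laser use are prognostic, the power changes agree to within 0.1 point. A separate simulation (60 evaluable, prevalences 0.5, 0.4 and 0.5) gave the same pattern: at 20%, power 68.5% without the factors and 76.4% with them. Its R² was the share of baseline-adjusted variance.

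**If the factors also predict pre-surgical pain.** Suppose they explain a share q of baseline VAS, acting in the same direction as on the outcome, and the overall correlation stays at 0.3. The share they add beyond baseline is (√R² − 0.3√q)² / (1 − q). For q = 10% and 20%:
- R² = 10%: (0.316 − 0.095)² / 0.9 = 5.4% and (0.316 − 0.134)² / 0.8 = 4.1%.
- R² = 20%: (0.447 − 0.095)² / 0.9 = 13.8% and (0.447 − 0.134)² / 0.8 = 12.2%.

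Simulation under this condition gave gains of about +1 to +2 points at R² = 10%, +4 to +6 at 20%, and under 1 point at 5%.

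**With the plan's own design factor of 0.7** in place of 0.91, 60 evaluable patients, and R² taken as a share of baseline-adjusted variance, power by noncentral t is 77.9% without the factors. With them it is 77.9%, 79.9%, 82.0%, 86.2% and 90.3% at R² of 0%, 5%, 10%, 20% and 30%. The conclusion does not depend on which design factor is used. The gap between about 67% and the planned 80% in the table is a separate sample-size question and is not counted here.

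**The case against.** The strongest reply is that nothing has been excluded. Section 12.4 speaks of ANCOVA in general terms and promises a detailed SAP, which is where a full covariate list would normally go. Validity is not threatened, the gain rests on an R² that appears nowhere in the documents, and the larger gains need factor effects close to the whole target difference. Different analgesia by site and technique could even out pain scores between groups as easily as separate them. The primary time point is also unsettled: the synopsis refers to 30 days and section 12.2.1 lists six post-operative days. Factors that predict early pain may not predict pain at day 30.

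Much of this stands as a limit on size. R² is unknown, 0% to 10% is the safer part of the range, and correlation between the factors and pre-surgical pain shrinks the gain. It does not remove the point. Section 12.4 presents its methods as those to be used and names one covariate. Followed as written, that model ignores the factors on which the arms were balanced. The stakes are also uneven: about half a point of power if the factors explain nothing, against several points if they matter moderately. Fixing the list now also avoids a later choice that could look driven by the data.

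On the mismatch between sections 4 and 7, the open wording of section 12.1 is compatible with three factors. It softens the inconsistency but does not correct section 4.

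**Conclusion.** The concern holds. The primary model as described omits the three minimisation factors. If they predict VAS pain, its standard error is overstated by about 2% to 10% at assumed R² of 5% to 20%. Adding them would then gain about 1.7 to 8.5 points of power, with baseline unrelated to the factors. If the factors explain 10% to 20% of pre-surgical VAS as well, the gain falls to under 1 point at R² = 5% and about 4 to 6 points at 20%. At R² = 0 the cost is about 0.5 points. These figures also rest on the assumed coin probability and prevalences. This is an efficiency matter that should be corrected, not a threat to the validity of the result.

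**What to change.** State in section 12.4, and carry into the SAP before any analysis, that the primary ANCOVA includes treatment, pre-surgical VAS and the three minimisation factors, coded as in the algorithm: subsite (oral cavity/oropharynx), concurrent neck procedure (yes/no) and laser use (yes/no). Amend section 4 so that it names the same three factors as section 7.

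The cost is one sentence in section 12.4 and the SAP, and one in section 4. The model uses three more degrees of freedom (55 residual instead of 58 with 61 patients). No new data are needed, because all three factors are recorded in order to randomise. The sample size of 64 does not change on this account.
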